10.2. Key Secondary Efficacy Endpoints and Analysis

The same analyses as described in Sections 10.1.1, 10.1.2 and 10.1.3 will be performed for the key secondary endpoints on the ITT population (both Full population and population with baseline PP NRS ≥ 7). Key secondary endpoints are defined as follows:

- Proportion of subjects with an improvement of PP NRS ≥ 4 at Week 16
- Proportion of subjects with PP NRS < 2 at Week 16

CCI

This document is confidential.

CCI

Same with primary endpoints, additional summary tables for key secondary endpoints will be presented by visit but excluding subjects from the visit summarized if the visit was affected by pandemic.

As a sensitivity analysis, summary tables for key secondary endpoints will be presented by visit but using weekly average PP/SD NRS with at least 2 non-missing diary and also with at least 3 non-missing diary, respectively. No analysis visit window extension at Week 16 applies.

Further details regarding IGA, EASI-75, PP NRS and CCI can be found in Sections 10.3.1, 10.3.2, 10.3.3 and 10.3.4.

In addition, forest plots will be presented for co-primary and key secondary endpoints on the ITT population.

10.3. Secondary Efficacy Endpoints and Analysis

Secondary efficacy endpoints during Initial Period:

Secondary endpoints during Initial Period will be analyzed for both populations (Full population; Baseline PP NRS ≥ 7) on the ITT population.

If a subject received any rescue therapy, the data on or after receipt of rescue therapy will be considered as treatment failure.

Hypothesis testing of between group treatment differences will only be applied to endpoint variables. All other variables, e.g. IGA, will be summarized descriptively.

Binary endpoints will be analyzed using a Cochran-Mantel-Haenszel test adjusted for the randomized stratification variables (IGA severity [3=moderate, 4=severe] and PP NRS ≥ 7 , < 7] for full population; IGA severity only for Baseline PP NRS ≥ 7 population). Any subjects with missing data at respective Weeks will be regarded as a non-responder.

Analysis methods for continuous and QoL endpoints are listed in Table 10-1 below.

Continuous and QoL endpoints (change from Baseline to each visit) will be analyzed using an analysis of covariance (ANCOVA) including treatment group and randomization stratification variables as factors and appropriate Baseline values as a covariates, if applicable. Missing values will be imputed using MI under MAR assumption (see Appendix 22.1). The least squares means, estimated standard error, and 95% confidence interval (CI) for each endpoint will be presented for each treatment group and analysis visit. The estimated treatment difference for each endpoint at each analysis visit will be summarized by presenting the difference in least squares means between treatment groups, the two-sided 95% CI, and associated p-value. In addition, change from Baseline to each analysis visit in EASI, PP-NRS, CCI, CCI and percent change from Baseline in PP-NRS and CCI will be analyzed using a MMRM approach, including terms of treatment group, stratification variables, appropriate Baseline values, visit, and interactions between baseline score with visit and treatment group with visit. Kenward-Roger approximation will be used to estimate denominator degrees of freedom. An unstructured covariance will be used to model the within-patient errors in the analysis. If calculation within proc mixed for unstructured covariance not possible for "Type=UN" then use instead "Type=CS". A linear contrast will be used, within the MMRM framework, to estimate difference between nemolizumab and placebo. The least squares

This document is confidential.

means, estimated standard error, and 95% CI for each endpoint will be presented for each treatment group and scheduled analysis visit. The estimated treatment difference for each endpoint at each visit will be summarized by presenting the difference in least squares means between treatment groups, the two-sided 95% CI, and associated p-value. CCI

[Redacted text block]

Table 10-1 Analysis Methods

Continuous/QoL Endpoints in Initial Period	Analysis Method
EASI	ANCOVA using MI-MAR, MMRM
PP NRS	ANCOVA using MI-MAR, MMRM

CCI [Redacted text block]

All efficacy endpoints of the Initial Period will be summarized by treatment and analysis visit.

Secondary Endpoints During Maintenance Period:

All secondary endpoints of the Maintenance Period will be descriptively summarized by treatment group at each analysis visit for the ITT population.

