10.3.2. Eczema Area and Severity Index (EASI)

The EASI is a validated measure commonly used in clinical trials and clinical practice to assess the severity and the extent of AD signs. The EASI score is a composite score ranging from 0 to 72 (see Table 6). The severity of erythema, induration/papulation, excoriation, and lichenification will be assessed by the investigator or trained designee on a scale of 0 (absent) to 3 (severe) for each of the 4 body areas: head/neck, trunk, upper limbs, and lower limbs, with half points allowed. In addition, the extent of AD involvement in each of the 4 body areas will be assessed as a percentage by body area of head, trunk, upper limbs, and lower limbs, and converted to a score of 0 to 6. The EASI score will be calculated (see Table 10-3).

Table 10-3: Eczema Area and Severity Index (EASI)

Body region	EASI score
Head/Neck (H)	$(E + I + Ex + L) \times \text{Area} \times 0.1$
Upper limbs (UL)	$(E + I + Ex + L) \times \text{Area} \times 0.2$
Trunk (T)	$(E + I + Ex + L) \times \text{Area} \times 0.3$
Lower limbs (LL)	$(E + I + Ex + L) \times \text{Area} \times 0.4$
EASI =	Sum of the above 4 body region scores

EASI-50, EASI-75 and EASI-90 are defined as a $\geq 50\%$, $\geq 75\%$, $\geq 90\%$ improvement in EASI from Baseline, respectively.

During Initial Period:

EASI will be collected at Screening, Baseline, Week 4, Week 8, Week 12, Week 16 and Early termination of the Initial Period.

EASI will be summarized as a continuous variable at each analysis visit. Absolute change and percent change from Baseline for the EASI score will also be included in the summary for ITT and PP population.

Change from Baseline in EASI at each analysis visit up to Week 16 will be analyzed using ANCOVA, with missing values imputed using MI under MAR assumption, and MMRM. For the MI and MMRM analyses the least squares means (LSMeans), standard error of LSMeans, and 95% CI for change from Baseline, as well as the difference in LSMeans between the treatment groups, the two-sided 95% CI, and associated p-value will be presented. In addition, percent change from Baseline in EASI at each analysis visit up to Week 16 will be analyzed using MMRM.

This document is confidential.

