10.3.3. Pruritus Numeric Rating Scale (NRS)

The Pruritus NRS is a scale to be used by the subjects to report the intensity of their pruritus (itch) during the last 24 hours. Peak pruritus (PP NRS) is an assessment of the maximum itch intensity in that Period while average pruritus (AP NRS) provides a measure of overall pruritus intensity.

Subjects will be asked the following question:

- For maximum itch intensity (PP NRS): “On a scale of 0 to 10, with 0 being ‘no itch’ and 10 being the ‘worst itch imaginable’, how would you rate your itch at the worst moment during the previous 24 hours?”
- For average itch intensity (AP NRS): “On a scale of 0 to 10, with 0 being ‘no itch’ and 10 being the ‘worst itch imaginable’, how would you rate your itch overall during the previous 24 hours?”

The screening PP/AP NRS will be determined by a single assessment using the PP/AP NRS (score ranging from 0 to 10) for the 24-hour Period immediately preceding the screening visit. The Baseline PP/AP NRS will be determined based on the average of daily PP/AP NRS (score ranging from 0 to 10) respectively during the 7 days immediately preceding Baseline (rounding to nearest whole number is not permitted). A minimum of 4 daily scores out of the 7 days immediately preceding Baseline is required for this calculation. PP/AP NRS at all follow-up visits will be determined in the same manner. Refer the details for the analysis visit window for diary data in Section 8.4. Subjects will receive instructions on how to record their PP/AP NRS scores and will complete the assessment once daily in the evening throughout the clinical study (including the run-in and the Follow-up Period).

In case of diary data, if the date of rescue therapy use is within the analysis visit window, the subject at the analysis visit will be treated as treatment failure except for OC analysis, and the weekly average will be imputed using the worst-case value for analysis

During Initial Period:

PP NRS will determined by an average as described above at every week from Baseline to Week 16 as a continuous variable for the Initial Period.

Descriptive summary of PP NRS will be provided for ITT and PP populations. Absolute change and percent change from Baseline for the PP NRS score will also be included in the summary.

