22.2. Example SAS Code

1. The example SAS code for CMH model is listed as below:

```
Proc freq data=analysis_data;  
  
    Tables stratum*trt*resp/ cmh alpha=0.1;  
Run;
```

2. The example SAS code for MMRM model is listed as below:

```
Proc mixed data = analysis_data;  
  
    class stratum trtp avisit subjid;  
    model chg = base stratum trtp avisit trtp*avisit base*avisit / ddfm=kr;  
    repeated avisit / subject=subjid(trtp) type=un;  
    lsmeans trtp/ cl diff;  
    lsmeans trtp*avisit/ slice=avisit cl diff;  
run;
```

3. The example SAS code for ANCOVA model is listed as below:

```
Proc mixed data = analysis_data;  
    class stratum trtp;  
    model chg = base stratum trtp;  
    lsmeans trtp/ cl diff;  
run;
```

4. The example SAS code for imputation phase by PROC MI:

```
proc mi data=analysis_data seed=118169 minimum=0 maximum=xx nimpute=50 out=out_data;  
    mcmc impute=monotone nbiter=200 niter=100;  
    var base stratum y4 y8 y12 y16;  
run;  
  
Proc mi data = analysis_data seed=118169 minimum=0 maximum=xx nimpute=number_of_imputations  
out=out_data;  
    class trtp stratum;  
    monotone reg (/details);  
    var base stratum y4 y8 y12 y16;  
run;
```

This document is confidential.

For IGA,

```
Proc mi data = analysis_data seed=118169 minimum=0 maximum=xx nimpute=number_of_imputations
out=out_data;
  class trtp stratum;
  monotone logistic (/details);
  var base stratum y4 y8 y12 y16;
run;
```

5. The example SAS code for pooling phase for ANCOVA model by PROC MIANALYZE:

```
proc sort data=diff; by avisitn trtp; run;
proc sort data=ism; by avisitn trtp; run;
proc mianalyze data=diff; by avisitn trtp;
modeffects estimate;
stderr stderr;
ods output ParameterEstimates=estdiff; run;
```

```
proc mianalyze data=ism; by avisitn trtp;
modeffects estimate;
stderr stderr;
ods output ParameterEstimates=estism; run;
```

1.0

CD14152.SPR118169.SAP.V01

Approved 10-Nov-2022 00:00:00

This document is confidential.

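### If the unstructured MMRM cannot be fitted, the SAP goes straight to compound symmetry, whose pooled variance gives a wrong Week 16 standard error whenever spread changes over time

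*SAP*

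**What the plan says.** SAP 10.3 sets the main structure: "An unstructured covariance will be used to model the within-patient errors in the analysis". For inference, "Kenward-Roger approximation will be used to estimate denominator degrees of freedom". The fallback is a single step: "If calculation within proc mixed for unstructured covariance not possible" "for 'Type=UN' then use instead 'Type=CS". The example MMRM code in SAP 22.2 has only "repeated avisit / subject=subjid(trtp) type=un", with no empirical (sandwich) option and no alternative structure.

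The number of visits differs by endpoint. Under SAP 10.3.3, PP NRS is derived "at every week from Baseline to Week 16 as a continuous variable for the Initial Period", which makes 16 post-baseline visits. For the other main endpoint, "EASI will be collected at Screening, Baseline, Week 4, Week 8, Week 12, Week 16" (SAP 10.3.2), which makes 4. Initial-period secondary endpoints are analysed in the full ITT population and again in subjects with baseline PP NRS of at least 7, for whom SAP 4.1 guarantees only 250 randomized.

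Change from baseline in EASI and PP NRS is analysed by ANCOVA with multiple imputation, with MMRM in addition. Percent change in both scores (SAP 10.3.2 and 10.3.3) and the individual EASI components (10.3.2) are assigned to MMRM only.

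**The concern.** CS has two parameters: one variance and one correlation for all visits. It cannot represent a spread that changes between Week 1 and Week 16, or a correlation that decays with the gap between visits. Falling from the most flexible structure to this one attaches an average variance to Week 16, the visit of most interest. If spread grows, the Week 16 interval is too narrow and its p-value too small; if spread shrinks, the reverse holds. Kenward-Roger adjusts for uncertainty in the covariance estimates but takes the fitted structure as true, so it does not correct this.

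Growth in spread is plausible in this trial because SAP 8.3 replaces scores on or after rescue with the worst possible value. As rescue use accumulates, more subjects sit at 10 while others improve. The documents do not show that it happens.

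**Working it through.** The plan states no SD, visit correlation or standard error for the MMRM, so there is no planned figure to reproduce. **All SDs and correlations below are assumptions.**

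**Inputs from the documents.** 750 subjects at 2:1, so 500 and 250 (SAP 4.3); 15% dropout by Week 16 (protocol 10.2); 16 weekly PP NRS visits and 4 EASI visits; two-sided 5% tests (SAP 8.1).

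**Parameter counts.** Unstructured: 16 × 17 / 2 = 136 for PP NRS and 4 × 5 / 2 = 10 for EASI. CS: 2.

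**Formula, complete data.** The Week 16 treatment difference has true SE = SD₁₆ × √(1/500 + 1/250) = SD₁₆ × 0.0775. CS replaces SD₁₆ by the root mean variance over visits, so

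ratio = √(mean visit variance) / SD₁₆, and actual error = 2 × [1 − Φ(1.96 × ratio)].

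For an SD moving linearly from a to b over 16 visits, mean variance = ((a + b)/2)² + 0.0944 × (b − a)², where 0.0944 = (16² − 1)/(12 × 15²).

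| SD, first visit to Week 16 | Mean variance | Ratio | Actual error at nominal 5% |
|---|---|---|---|
| 1.3 to 2.6 | 3.8025 + 0.1596 = 3.962 | 1.990/2.6 = 0.766 | 13.3% |
| 1.6 to 2.6 | 4.41 + 0.0944 = 4.504 | 2.122/2.6 = 0.816 | 11.0% |
| 2.0 to 2.6 | 5.29 + 0.0340 = 5.324 | 2.307/2.6 = 0.887 | 8.2% |
| flat | b² | 1.00 | 5.0% |
| 2.5 to 2.0 | 5.0625 + 0.0236 = 5.086 | 2.255/2.0 = 1.128 | 2.7% |

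**Check by simulation.** For SD 1.5 to 2.5 the formula gives ratio 0.81 and 11.3% error. In 4,000 complete-data runs the mean CS standard error was 0.157 against an empirical SD of 0.193. Rejection was 11.2% with CS and 5.4% with the Week 16 variance. Kenward-Roger itself was not run; at this sample size its correction is negligible.

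**With 15% dropout.** A large-sample likelihood fit for SD 1.5 to 2.5 gave ratios of 0.78 to 0.80 (11.8% to 12.8%). Flat SD gave 0.96 to 1.00, and SD 2.5 to 2.0 gave ratios from 1.08 upwards. In a separate 1,000-run simulation (500:250, lag-1 correlation 0.9), the three rising rows of the table gave 14.8%, 13.2% and 8.7%. Constant SD gave 6.2%, so about one point of the excess need not come from growing spread; the Monte Carlo error is itself about one point.

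**Worst-score rule.** Let a fraction f be rescued and scored 10, and let the rest have mean m and SD 2.0. Then overall SD = √[(1 − f) × 4 + f(1 − f)(10 − m)²]. With f = 5% and m = 5 this is √(3.8 + 1.1875) = 2.23. With f = 15% and m = 4 it is √(3.4 + 4.59) = 2.83. These are SDs of the score, with assumed rescue rates. They show that growth is possible, not that it occurs.

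**After a change of structure.** Heterogeneous CS, with its own variance at each visit, was fitted where the true correlation was autoregressive and the SD rose. It gave ratios of 1.04 to 1.08 with 16 visits and 1.01 to 1.03 with 4. Actual error was 3.4% to 4.7%, slightly conservative.

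**The case against.** The strongest reply is that the fallback may never be used. A count of 136 parameters does not show that the fit will fail. Even the smallest guaranteed population keeps about 250 × 0.85 = 212 subjects at Week 16. In simulated Gaussian data with 16 visits, 250 or 400 subjects, 15% monotone dropout and 5% intermittent missingness, an unstructured fit by EM converged to a positive-definite matrix in 600 of 600 runs. That is neither PROC MIXED nor real diary data, but it means failure should be treated as a contingency that the SAP itself provides for, not as an expectation.

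Second, the direction is not documented. PP NRS is bounded at 0 and 10, no SDs by visit are given, and with a falling SD CS is conservative.

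Third, little rests on these models. The co-primary and key secondary tests are CMH, other secondary comparisons are not adjusted for multiplicity, and visit-by-visit ANCOVA with multiple imputation covers change in EASI and PP NRS without pooling variance across visits. The rule is also deterministic, which is a merit.

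All three points stand as limits on likelihood and impact. They do not make CS a good fallback. Percent change in weekly PP NRS combines 16 visits with an MMRM-only analysis, so there the ANCOVA offers no cross-check.

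**Conclusion.** The point holds conditionally. If the unstructured fit fails, CS with model-based errors misstates the Week 16 standard error whenever variability changes over visits. Under assumed linear growth without dropout, actual error is about 8% (SD 2.0 to 2.6), 11% (1.6 to 2.6) or 13% (1.3 to 2.6). The last case requires the SD to double. With flat SD and no dropout it is about 5%. With SD falling from 2.5 to 2.0 the standard error is overstated by about 8% to 13%.

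A reader might infer that the Week 16 MMRM p-values will be anti-conservative, or that the trial's type I error is inflated. The documents support neither. They do not show that the unstructured model will fail or that spread grows, and no multiplicity-controlled test uses this model. What is exposed is a set of supportive intervals and p-values, chiefly for weekly PP NRS. EASI and its components are also covered by the rule, but with 4 visits they are unlikely to trigger it. This is an inexpensive improvement, not a threat to the main conclusions.

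**What to change.** Replace the fallback sentence in SAP 10.3 with a pre-specified order of structures that allow visit-specific variances, taking the first that converges. For example: unstructured, then heterogeneous Toeplitz (16 variances + 15 correlations = 31 parameters for PP NRS), then heterogeneous AR(1) or heterogeneous CS (16 + 1 = 17). Use plain CS only last, and then with empirical (sandwich) standard errors. Mirror this in the example code in SAP 22.2, and ask that each output state the structure used.

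Heterogeneous CS alone already removed the understatement in the check above. The earlier steps were not simulated; they are listed because they also allow correlation to vary with the gap between visits.

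The cost is one SAP sentence and a few lines of code. The downside is that Kenward-Roger degrees of freedom are not available with sandwich errors, so the SAP should name the method to use in that last step. The order stays deterministic, so no choice of structure is left open after unblinding.
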